## Study Endpoints

#### Primary Safety/Tolerability Endpoint:

Safety/Tolerability will be assessed by the non-inferiority of incidence of serious adverse events (SAEs), unanticipated SAEs(USAEs), device-related SAEs (DSAEs) and Unanticipated Device Related SAEs (UDAEs) that are associated with the TENS therapy throughout the stimulation and the follow-up period versus historical control (compared with other TENS systems).

Safety variables will be tabulated and presented for all subjects including enrolled, but discontinued, subjects. Number of subjects undergoing active stimulation and any reasons for discontinuation of study treatment will be tabulated.

#### Primary Effectiveness Endpoint:

The primary efficacy endpoint is the percent reduction in total body weight loss (%TBWL), measured as End Weight – Initial Weight divided by Initial Weight, multiplied by 100, at the end of Therapy period compared to Baseline between Treatment and Control.

Secondary Effectiveness Endpoints:

Number of subjects reporting >5% total body weight loss at the end of Therapy compared to Baseline between Treatment and Control

Percent change in appetite scores at the end of Therapy period compared to Baseline between Treatment and Control.

Blood pressure, blood lipids, CMP (Reduction in ALT) and HbA1c at the end of Therapy compared to Baseline between Treatment and Control groups.

% changes in BMI at the end of Therapy compared to Baseline between Treatment and Control groups

#### **Ancillary Endpoints:**

Changes between the following values:

Ease of use/prevalence of use errors associated with the patch unit and dietary application during initial training.

Subject preference scores at the end of Therapy compared to Baseline between Treatment and Control groups.

## Statistical Analysis

Categorical variables will be summarized by number and percent. Continuous variables will be summarized by total number (N), mean, standard deviation (SD), median, minimum and maximum. Ninety-five percent, 2-sided confidence intervals on estimated means and differences in means between treatment and control groups will be calculated (corrected for multiplicity where needed). Confidence intervals will be similarly computed for proportions and differences between proportions. In addition, propensity score and sensitivity analyses will be utilized to compare adverse events and adverse device effects incidence versus historical control. Wilcoxon signed rank tests, Fisher exact tests, and Pearson Correlations will be utilized to compare changes in baseline variables between varying time points of the study (e.g. Baseline versus Therapy) and to correlate stimulation parameters with endpoint values.

Markov-chain Monte Carlo Analyses will be utilized to conduct Bayesian posterior probability distributions with multiple imputations allowed to assess treatment efficacy within and between cohorts. The need for additional endpoints to achieve primary and secondary significance will be determined utilizing longitudinal modeling. Finally, dose response will be modeled and analyzed within and between cohorts to determine optimal therapy dose for stimulation in open label period within and between cohorts using Normal dynamic linear modeling (NDLM) since monotonicity of the response cannot be assumed.

#### Risk/Benefit Analysis

If shown to be safe and effective, the therapy could eventually provide overweight/ moderately obese subjects a low risk option for weight control beyond diet and lifestyle modification alone.

The potential adverse events and adverse device effects and risks associated with this study and the use of the patch System are identical to those normally associated with standard TENS system used for pain control and similar indications.

#### 1. INTRODUCTION

#### 1.1 BACKGROUND

According to the Centers for Disease Control (CDC) up to 35% of adults over the age of 20 are obese, meaning they have a body mass index (BMI) of over 30 kg/m² while up to 69% of similarly aged adults are overweight, meaning they have a BMI of 25-30 kg/ m² (¹; Appendix 1). Individuals who are overweight or obese are at high risk for adverse impacts to quality of life (QOL) factors including general health (²), pain (³) and psychosocial status (⁴). However, losing weight via calorie restriction dieting is notoriously difficult for such individuals (²). Sustained loss of even 5-10% of weight is uncommon with most dieters (², ³) with most regaining nearly half of the lost weight after one year (⁴). While the precise physiological, sociological and genetic factors associated with weight gain and weight loss remain an area of intense investigation, what is becoming clear is that sustained weight loss requires long term calorie intake reduction (²), which, in turn, appears to require, among other factors, appetite control (², ⁴). The purpose of the present non-significant risk (NSR) study is to investigate the effect of transcutaneous electrical nerve stimulation (TENS) on weight loss in overweight-to moderately (i.e. Type 1) obese individuals (i.e. BMI of 25 to 35 kg/ m² inclusive 15,16; Appendix 1) with a long-term goal of determining if such an approach may be of benefit in assisting such individuals in achieving their weight loss goals.

#### 1.2 PENS AND TENS FOR WEIGHT LOSS

Transcutaneous electrical nerve stimulation (TENS) involving the delivery of electrical current to subcutaneous nerve branches via an electrode placed on the skin surface is a well-established treatment modality for muscle pain, muscle atrophy and spasms as well as for pain associated with a variety of conditions including diabetic neuropathy. More recently this modality has been shown to be effective in treating certain symptoms associated with migraine headaches by delivering electrical stimulation to branches of the trigeminal nerve (8). A related therapy, Percutaneous Electrical Nerve Stimulation (PENS), in which electrode is inserted into the epidermis, is now in general medical usage for the treatment of urinary incontinence, fecal incontinence, and back pain (5-8).

The clinical evidence for a PENS effect on appetite and weight loss is provided by Ruiz-Tovar's study which demonstrated significant weight loss for PENS stimulation of dermatome T6 (the area of skin supplied by cutaneous branches of a single cranial or spinal nerve) via appetite suppression in a European sham control study of 105 subjects (). Similar preliminary clinical results utilizing TENS have been reported in appetite control and subsequent weight loss by [name], a Stanford University researcher, who was granted a method patent (Transcutaneous Electrical Nerve Stimulator for Appetite Control) for his invention that uses TENS to stimulate the thoracic spine area at T6–T10. Each of these studies utilized obese subjects and provided stimulation only during in-clinic supervised sessions. The present study is designed to extend these preliminary studies by utilizing TENS in overweight-to Type 1 obese-subjects (i.e. BMI of between 25 and 35 kg/ m² inclusive ) stimulating in an outpatient/at home setting using a wearable, patch TENS system.

## 1.3 THE HYPOTHESIZED MECHANISM OF T6/T7 STIMULATION FOR APPETITE SUPPRESSION AND WEIGHT LOSS

The effect of PENS, and presumably, TENS, has been widely demonstrated by posterior tibial nerve neurostimulation in treating urinary and fecal incontinence, creating a somato-autonomic reflex (; Figure 1). The definition of a somato-autonomic reflex is a reflex elicited by stimulation of somatic tissue (strictly speaking, tissue of the musculoskeletal system and the dermis of the skin), and manifesting as an alteration of the autonomic nervous

[figure not shown]

Figure 1: Somato-Autonomic Reflex Arc

system function (Figure 1). Altered autonomic nervous system functions may lead to changes in the function of dependent organs (like the stomach and other gastrointestinal organs), a situation sometimes referred to as a Somato-visceral reflex. To the PI's knowledge, the study cited by Ruiz-Tovar is the first to report using PENS of dermatome T6 to reduce appetite and, consequently, obtain a clinically-significant weight loss (9). It is likely that the effect is produced by the creation of a Somato-autonomic reflex in similar fashion to percutaneous electrical stimulation of the posterior tibial nerve in treating incontinence, but in this case suppressing appetite (10).

As supported by [name] preliminary results (9), it is likely that similar results to PENS can be obtained using TENS to stimulate the same region, given the shallow 2 to 4 millimeter depth of sensory afferents throughout the target dermatome. Chen reported that electric gastric stimulation with a gastric pacemaker may affect the central nervous system by segregating hormones in the stomach and regulating satiety and/or appetite, with ghrelin being particularly involved in this mechanism (11). As shown by Ruiz-Tovar's study, the electric stimulation's main effect is appetite reduction. This study consisted of 105 subjects divided into 3 groups. Group 1 included 45 subjects who underwent dermatome T6 stimulation and maintained a 1,200 calorie diet and who were scheduled for bariatric surgery. These subjects had BMIs of greater than 40 or greater than 35 with co-morbidities. Group 2 included 45 subjects that maintained a 1,200 calorie diet only and who were scheduled for bariatric surgery. These subjects also had BMIs of greater than 40 or greater than 35 with co-morbidities. Group 3 included 15 subjects with a BMI greater than 30 who received sham stimulation (at the ankle) and who maintained a 1,200 calorie diet. Group 1, the treatment arm, evidenced dietary compliance in excess of 90% and achieved a significant weight loss success (equal to or greater than 5 kilograms (11 pounds) in 76.7% of subjects, as compared to Groups 2 and 3 where weight loss success was less than 6.7% and 0.0%, respectively. No complications were observed associated with the technique.

It thus appears likely that, through safely stimulating T6/T7 via TENS, a Somato-visceral reflex arc will be activated which will suppress appetite and support eventual weight loss in overweight and obese subjects.

#### 2. STUDY RATIONALE

The purpose of the present study is to determine the safety and effectiveness of stimulation via a wearable patch TENS system of the T6/T7 dermatome on appetite suppression in adult (18 to

65 years of age inclusive), overweight/obese subjects (i.e. a BMI of 25 to 35 kg/m² inclusive , Appendix 1) who desire to lose weight. The study will seek thus to extend existing data on the use of dermatomal stimulation on obese and morbidly obese patient to subjects who are overweight/obese (i.e. a BMI of 25 to 35 kg/m² ; Appendix 1).

#### 2.1 JUSTIFICATION FOR STUDY GIVEN RISK/BENEFIT OUTCOME

Up to 35% of adults over the age of 20 in the United States are overweight. Being overweight places individuals at higher risk for a number of what are termed metabolic disorders including diabetes mellitus. This risk association is thought to be the reason for the high health care costs associated with overweight and obesity. While diet and exercise do show efficacy in a substantial subset of subjects, long term weight control is difficult to achieve for the vast majority of overweight individuals. The physiological and psycho-social reasons for this are not well characterized and likely highly complex, but a key component of this challenge is associated with appetite control. The present study seeks to determine if a method of appetite control utilizing T6/T7 dermatome stimulation in obese individuals can be utilized to the broader overweight population. The study utilizes non-invasive TENS stimulation within the range of the energy delivery well known to be safe for at-home use for nerve and muscle pain. Subjects will be informed of all potential side effects related to stimulation prior to enrollment and, throughout the study, subjects will be monitored and allowed to decrease or discontinue stimulus if any such side effects are deemed to be intolerable for participants.

In addition, since appetite and weight loss can be affected by a variety of physiological and psychosocial factors (12,13, 15, 17), the change in appetite will be measured weekly using a validated tool, the Visual Analog Scale (VAS; See Appendix 3) and also assessed at baseline at the end of the study via administration of the Three Factor Eating Questionnaire R-18 V2 (TFEQ-R1V2). Please note that while the VAS was first developed for pain, it has been validated for weight loss/appetite applications (14) while the TFEQ-R18V2 has specifically been validated in weight loss applications (17, 18). The present study is not intended to be a formal validation of the assessment tool's applicability to the population targeted by the present study per se; it is intended simply as an assessment of potential changes in such parameters correlated with delivery of therapy during the study. Thus, the use of the tool as presented is considered scientifically valid.

Thus, the non-significant risk of the study is more than balanced by the potential societal benefit of the development of this novel, non-invasive appetite control method.

#### 3. DEVICE DESCRIPTION

The TENS System consists of:

TENS Unit (Appendix 2)	ELIRA wearable Patch
Electronic Diary tool (Appendix 5)	Diary/dietary application running on and Android Smart- phone:
	4.5" 720p HD TFT display Size (LWH): 2.6 inches, 0.46 inches, 5.1 inches Weight: 4.96 ounces
Device Accessories	Extra packs ELIRA electrodes  Device/Phone Chargers
	Electronic Scale
	Plastic Phone Cover and System Pack

Other study accessories

TENS Clean-Cote Skin Wipes, **ALCOHOL** prep pads, Cetaphil Moisturizing Lotion

#### 4. STUDY OBJECTIVES

The objectives of this study are to demonstrate safety and effectiveness of a wearable patch TENS system (Appendix 2) in driving weight loss when coupled with an integrated weight loss reduction strategy. The study is designed to demonstrate that TENS stimulation sufficient to drive weight loss is safe and tolerable when compared to standard of care, and that adverse events/adverse device effects are similar to other TENS device use cases.

#### 5. STUDY DESIGN

Randomized, adaptive parallel arm study. Subjects will be initially screened during a screening period (1 week, ±7 days; Figure 2). During this screening period, prior to study procedures being performed, subjects will sign an informed consent form. Then they will have their

[figure not shown]

Figure 2: Study Outline

weight and blood pressure measured, FOCBP will have a pregnancy test, get blood drawn for analysis (blood lipids, CMP, hemoglobin A1c), and complete patient preference questionnaires. At the end of the screening/baseline period, eligible subjects will be offered the chance to enroll in the study. After enrolling, subjects will be randomized to treatment or control groups.

The Treatment group will be instructed to follow a healthy 1200 calorie diet that they will follow for the duration of the study and will receive training on the use of the weekly paper diary, electronic scale, smartphone app and the Elira wearable patch system. All treatment subjects will be required to stimulate in the office for a period of time to confirm sufficient system training and tolerability of the stimulation. Following this, subjects will enter the Therapy Period, for a 12-week duration.

The Control group will be instructed to follow a healthy 1200 calorie diet that they will follow for the duration of the study and will receive training on the use of the weekly paper diary and electronic scale. The Control group will not receive the electronic smartphone app or the Elira wearable patch system.

At the end of the Therapy Period, subjects will be assessed for weight loss, blood pressure, CMP, blood lipids, HbA1c, and will be terminated from the study.

The study utilizes an adaptive approach where cohorts of enrolled subjects (in groups of 25 per arm) are assessed for dose response and progression to achievement of primary and secondary endpoints. Frequent interim endpoint assessment utilizing Markov-chain Monte Carlo (MCMC) methods coupled with longitudinal analyses will be utilized to determine sample sizes for future cohorts (assessed primarily via Normal dynamic linear modeling [NDLM]).

#### 5.1 Dosing Schedule

All Treatment Subjects will be trained in rotation of the patch electrodes every 24h such that it is applied to varying locations on the T6/T7 dermatome. Each active therapy subject will receive up to 30 mA sustained current of stimulation (up to 40mA peak) for 30 minutes after each of three meals per day (delivered within 1-hour post prandially). Based on tolerance of the therapy, a subject may decrease his or her dose by dropping one of the 3 post prandial sessions after receiving approval from a clinical coordinator and/or PI. Subjects who do not experience sufficient appetite suppression may add up to three 15-minute pre-prandial rescue sessions delivered within 2 hours before each meal after receiving approval from a clinical coordinator and/or PI. The nominal stimulation dose per day for any subject will thus be 2400 mA (60 minutes at 40 mA) while the maximum dose for any given subject will be 5400 mA (135 minutes at 40 mA).

During the therapy period, Treatment Subjects will undergo initial assessments to ensure they are familiar with the device, the daily electronic diary, weekly paper diary, and the 1200 calorie diet. All subjects (Treatment and Control) will be required to undergo follow-up assessments at least once per every 4 weeks during the study. Up to two additional unscheduled visits per subject will be permitted during the study. PI will oversee any adjustments to treatment dosing or stimulation parameters.

#### 5.2 DATA COLLECTION:

All subjects will be asked to keep a VAS paper diary (hunger, appetite, well-being) in which they will record such values weekly. Subjects will record their diary variables. For treatment subjects, any adjustments to stimulation session schedule will be recorded within the electronic diary and by clinical coordinators.

#### 5.3 ASSIGNMENT & BLINDING

Subjects meeting the Inclusion and Exclusion criteria will be enrolled and randomized into either Treatment or Control groups. The randomization algorithm will be blocked to account for site bias and to ensure counterbalance across sites. As this is an open label study, there will be no consideration for blinding.

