	At the end of the Therapy Period, subjects will complete an end of study visit to be assessed for weight loss, blood pressure, blood lipids, hemoglobin A1c, CMP (Reduction of ALT), patient preference questionnaire and their participation will be considered complete (pending laboratory results, adverse events or serious adverse events).
	The study utilizes an adaptive approach where cohorts of enrolled/randomized subjects (in groups of 25 per arm) are assessed for dose response and progression to achievement of primary and secondary endpoints. Frequent interim endpoint

	assessment utilizing Markov-chain Monte Carlo (MCMC) methods coupled with Longitudinal analyses will be utilized to determine sample sizes for future cohorts (assessed primarily via Normal dynamic linear modeling [NDLM]).
Subject Population / Sample Size	The primary endpoint is powered at a final enrollment of 75 subjects per group, for a total of 150 subjects, but interim analyses based on Bayesian posterior probability distributions with multiple imputation will be utilized to assess interim significance.
	In the event the interim analysis is not significant, up to 300 subjects may need to be enrolled in order to achieve final separation between groups for statistical significance. Thus, Elira may need to screen up to 500 subjects to account for exclusions prior to enrollment.
Study Duration and Sites	Minimum study duration for each patient will be 13 weeks. As it is expected that recruitment of 150 subjects will take up to 12 weeks, the overall study duration is anticipated to be a minimum of 26 weeks, assuming all cohorts are enrolled. The study will be conducted at up to 10 centers.
Inclusion	Subject is between 18 – 65 years of age inclusive.
Criteria	Subject has a BMI of 25-35 kg/ m² inclusive.
	Subject has signed the informed consent form and is able to comply with study protocol and adhere to study visit schedule.
	Subject is able to wear and use a wearable, patch TENS system.
	Subject is able to use a touch screen hand held smart phone.
	Subject is fluent in English and can complete patient questionnaires.
	Subject can comply with a 1200 calorie diet for the duration of the study.
	Subject is male or non-pregnant, non-lactating female, who agrees to use effective contraceptive methods throughout the length of the trial based on PI approval.

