#### Visit Schedule

Screening/Baseline Visit 0 (-1 week; ± 7 days) – Obtain Informed Consent prior to any study procedures. Confirm subject has met all inclusion criteria and no exclusion criteria. History & Physical including height & weight, diet history, baseline clinical parameters, provide laboratory requisition, urine pregnancy test for women of childbearing potential (WOCBP), and questionnaires. Initiate subject weekly paper diary with training for weekly completion. Subjects will be instructed to return with their weekly paper diary(ies) at their next scheduled visit.

**Enrollment/Randomization Visit 1 (Day 0; ± 7 days)** – Confirm subject continues to meet all inclusion criteria and no exclusion criteria. Assessment of T6/T7 dermatomes, clinical parameters, BP, weight, perform urine pregnancy test for WOCBP if not done at screening, administer TFEQ-R18V2 Questionnaire, assess for adverse events and changes to concomitant medications. Subjects will be randomized based on the blocked randomization algorithm.

Treatment and Control subjects will be instructed to follow a healthy 1200 calorie diet throughout the study, an electronic scale with instructions on use will be provided, and a paper diary with training for weekly completion will be provided. Subjects will be instructed to return with their paper diary(ies) at the next scheduled visit.

Only the treatment subjects will receive a handheld smartphone with the custom application and an Elira wearable patch system. It is recommended for treatment subjects to utilize an TENS Clean-Cote Skin Wipes and/or alcohol prep pad to maintain a clean application area for the treatment. Treatment subjects will also receive Cetaphil Moisturizing Lotion to be used if any irritation occurs at the treatment site. Subject will

be instructed to notify site immediately if any irritation occurs. Treatment subjects will stimulate under the supervision of the investigator or coordinator for 30 minutes prior to being discharged with the device. Treatment subjects will be assessed for toleration of the stimulation to further evaluate dose adjustment. Treatment subjects will be discharged with the Elira wearable patch system & Smartphone App and instructions on use. Treatment subjects will be instructed to return with the Elira wearable patch system and smartphone app at their next scheduled visit.

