### 8. STATISTICAL CONSIDERATIONS AND ANALYSIS PLAN

Categorical variables will be summarized by number and percent. Continuous variables will be summarized by total number (N), mean, standard deviation (SD), median, minimum and maximum. Ninety-five percent, 2-sided confidence intervals on estimated means and differences in means between treatment and control groups will be calculated. Confidence intervals will be similarly computed for proportions and differences between proportions. In addition, propensity score and sensitivity analyses will be utilized to compare adverse events and/or adverse device effects incidence versus historical control. Wilcoxon signed rank tests, Fisher exact tests, and Pearson Correlations will be utilized to compare changes in baseline variables between varying

time points of the study (e.g. baseline versus post stimulation treatment) and to correlate stimulation parameters with endpoint values. Markov-chain Monte Carlo Analyses will be utilized to conduct Bayesian posterior probability distributions with multiple imputations allowed to assess treatment efficacy within and between cohorts. The need for additional endpoints to achieve primary and secondary significance will be determined utilizing longitudinal modeling. Finally, dose response will be modeled and analyzed within and between cohorts to determine optimal therapy dose for stimulation in open label period within and between cohorts using Normal dynamic linear modeling (NDLM) since monotonicity of the response cannot be assumed.

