#### 8.1.3 Weight Loss

The null and alternative hypotheses are:

$$H_0$$
:  $π_T ≤ π_C$ 
 $H_1$ :  $π_T > π_C$ 

Where  $\pi_T$  and  $\pi_C$  are the probabilities of weight loss (% TBWL, %EBWL) in treatment versus control respectively. Estimates of the proportion of weight loss in pounds, % total body weight loss (%TBWL) Excess Body Weight Loss (%EBWL) or BMI will be compared with a tested Fishers Exact Test. Estimates and 95% confidence intervals will also be computed for the difference in rate of weight loss between varying stimulation levels.

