#### 8.2 JUSTIFICATION OF SAMPLE SIZE

The calculated sample size for the study is based on conservative imputation of results from other studies on weight loss including the use of TENS for weight loss. The degree of coaching/dietary support throughout the present study is moderate intensity lifestyle/weight coaching. The sample size modeling assumes an average of 3.5% TBWL in Control subjects using diet and exercise alone. The estimated weight loss in the Treatment subjects is modeled from preliminary data on T6/T7 dermatomal TENS when used for weight loss: 7.5% TBWL. The variance of the responses in the study (i.e. Standard Deviation) was modeled at + 5% TBWL. This value was taken from previous dermatomal TENS weight loss study results. The model assumes a 30% drop out rate across groups and an 80% powered endpoint using an adaptive p spending model wherein interim posterior probability assessments are allowed after enrolling proscribe cohorts of not less than 25 subjects per group for not less than 7 weeks of stimulation. The alpha penalty will be minimized per interim by assessing the relationship between stimulation (i.e. dose) and weight loss using Normalized Linear Dynamic Modeling (NLDM) to determine overall sample size projected (i.e. futility) rather than assessing the primary endpoint hypothesis per se. Monotonicity will not be assumed in this analysis. This modeling provides an estimate of 75 subjects per group, for a total study size of 150 subjects. However, the protocol allows for enrollment of additional subjects should the interim model project under powering of the primary endpoint.

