#### 9.10 **DIET**

Subjects will be encouraged to maintain a healthy 1200 calorie diet throughout the study. The study doctor and/or research coordinator will provide guidance to assist the subjects on maintaining the diet.

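### Site is the blocking factor in the randomisation but is named in no effectiveness analysis; if sites differ in outcome, intervals are wider than needed and tests run below nominal level

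*Combined protocol and SAP*

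**What the plan says.** On allocation, Section 5.3 (Assignment & Blinding) states: "The randomization algorithm will be blocked to account for site bias and to ensure counterbalance across sites". The Visit Schedule in the Protocol Summary agrees: "Subjects will be randomized based on the blocked randomization algorithm". Block size is not given. The Summary also says: "The study will be conducted at up to 10 centers".

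On analysis, Section 8 says: "Ninety-five percent, 2-sided confidence intervals on estimated means and differences in means between treatment and control groups will be calculated". It extends this to proportions and does not say how the intervals are built. Section 8.1.3 says that the weight-loss measures "will be compared with a tested Fishers Exact Test", with no stratification. Section 8.1.2 gives rank tests for appetite, also without strata. Section 8 and the Summary add MCMC posterior analyses, longitudinal modelling and NDLM dose-response models, and list no covariates for any of them. Site appears in none of these passages.

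On why sites might differ, Section 9.10 leaves dietary support to local staff: "The study doctor and/or research coordinator will provide guidance to assist the subjects on maintaining the diet".

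**The concern.** The design treats site as a source of bias and balances the arms within it. That balance takes between-site variation out of the true sampling error of the arm difference. An analysis that ignores site still counts that variation in the estimated error. The interval is then wider than the design warrants, its coverage exceeds 95%, and the test rejects less often than its nominal level. The precision gained by blocking is lost at the analysis stage.

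The matter should be settled before data are seen. The trial is open label with interim looks, so adding site later could look data-driven.

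**Working it through.** **Inputs from the plan.** Section 8.2 gives control mean 3.5% TBWL, treatment mean 7.5% (difference 4.0 points), SD 5, dropout 30%, power 80% and 75 per group. The two-sided 5% level is implied by the 95% intervals; no numeric alpha is stated.

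**Assumed inputs.** The site share of outcome variance, ρ, is not in the documents and is taken as 0, 5, 10 and 20%. The simulation also assumes 10 equal sites of 15 and blocks of 4.

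**The plan's own figure.** With these inputs, n per arm = 2 × (1.96 + 0.84)² × 5² / 4² = 24.5, so 25, and 25 / 0.70 gives 36 after dropout. The stated 75 is not reproduced. The spending rule is unspecified, so the gap cannot be resolved here; it is a separate matter and nothing below depends on it. At 75 per arm, power for 4 points is 99.8%. At 52 completers per arm (75 × 0.70, rounded down) it is 98.3%.

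**Formula for %TBWL.** With arms balanced within site:

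- true variance of the difference = 2 × SD² × (1 − ρ) / n
- variance estimated without site ≈ 2 × SD² / n
- standard error ratio = 1 / √(1 − ρ)
- real two-sided size = 2 × [1 − Φ(1.96 / √(1 − ρ))]
- precision is that of a site-adjusted analysis on n(1 − ρ) subjects, so the share of subjects effectively lost is ρ

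Example at ρ = 10%: 1 / √0.90 = 1.054; 1.96 × 1.054 = 2.066; size = 3.9%.

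| Assumed ρ | SE overstated | Subjects effectively lost | Real coverage | Real size |
|---|---|---|---|---|
| 0% | 0% | 0% | 95.0% | 5.0% |
| 5% | 2.6% | 5% | 95.6% | 4.4% |
| 10% | 5.4% | 10% | 96.1% | 3.9% |
| 20% | 11.8% | 20% | 97.2% | 2.8% |

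**Simulation check for %TBWL.** 8,000 runs per setting, no dropout, unadjusted t interval against a linear model with site. Simulation error on a 5% size is about 0.24 percentage points (√(0.05 × 0.95 / 8000)).

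| ρ | Half-width without site | Half-width with site | Size without site | Size with site |
|---|---|---|---|---|
| 0% | 1.610 | 1.614 | 4.8% | 4.7% |
| 5% | 1.608 | 1.575 | 4.1% | 4.7% |
| 10% | 1.602 | 1.531 | 3.9% | 5.0% |
| 20% | 1.596 | 1.445 | 3.0% | 4.9% |

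With 30% of subjects removed at random, the half-width goes from 1.934 to 1.968 at ρ = 0, from 1.934 to 1.923 at 5%, from 1.931 to 1.874 at 10%, and from 1.917 to 1.763 at 20%. Random loss disturbs the within-site balance, so the gain shrinks, and at ρ = 0 adjustment has a small cost.

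**>5% responders.** If %TBWL is normal with the control values, the control rate is 1 − Φ((5 − 3.5) / 5) = 38%. Dichotomising dilutes the site share: latent shares of 5, 10 and 20% become about 3.1, 6.2 and 12.5% on the binary scale. Then 1 / √(1 − 0.031), 1 / √(1 − 0.062) and 1 / √(1 − 0.125) give standard errors overstated by about 1.6, 3.2 and 6.9%.

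**Power (simulated, 30% dropout).** At 4 points, power is 97.8% without site and 97.4% with it at ρ = 0, and 99.0% and 99.3% at ρ = 20%. At 2.75 points, the difference with about 80% power at 52 per arm, including site changes power from 80.5 to 79.1% at ρ = 0, from 81.9 to 83.8% at ρ = 10%, and from 81.6 to 86.1% at ρ = 20%.

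**The case against.** The strongest reply is that the consequence is conditional and mild. No between-site variance is given, all sites use the same 1200-calorie diet, and with no site effect there is nothing to correct. This stands: only the omission is certain, and its size is an assumption. A reader might infer that the plan's intervals are definitely too wide and that their 95% coverage is definitely wrong. The documents do not support that.

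A reader might also infer that every analysis excludes site. For the MCMC and NDLM models, and for the construction of the intervals, site is unmentioned rather than excluded. Only the Fisher test is unstratified as written.

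Nor do the documents state an error rate that is being missed. Section 8.2 refers to an "80% powered endpoint using an adaptive p spending model" without giving levels, so the sizes above refer to a fixed 5% test. The standard error ratio does not depend on the level.

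The %TBWL figures should not be carried over to other endpoints. The responder effect is smaller, and blood pressure, lipids, ALT, HbA1c and appetite are not quantified. The t interval in the simulation is also not named in the plan; it stands in for the planned difference in means.

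Dropout weakens the gain in the completer analysis. The modified intent-to-treat set with last value carried forward keeps more of the randomised subjects, so for that set the full-data figures are the closer guide.

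What remains is that a factor judged important enough to block on has no stated place in the analysis, and that following the Fisher test as written is conservative whenever sites differ.

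**Conclusion.** The point holds as a low-cost improvement, not as a threat to validity. If sites differ, ignoring site costs precision and makes tests conservative; it does not raise the false-positive risk. For %TBWL the loss is nil at a site share of 0, small at 5%, and material from about 10% (standard error overstated by 5.4%, rising to 11.8% at 20%). These figures rest on assumed site shares, near-exact balance within site and a two-sided 5% level inferred from the 95% intervals. Power at the planned 4-point difference is about 98% with or without site, so the benefit is in interval width and in detecting smaller true effects.

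**What to change.** In Section 8, state that the between-arm analysis of %TBWL is a linear model with arm and site, with small sites pooled by a rule fixed in advance. For >5% responders, replace the unstratified Fisher test by a site-stratified Cochran-Mantel-Haenszel test with a stratified difference in proportions. Say whether the MCMC and NDLM models include site.

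The cost is SAP wording and up to 9 degrees of freedom out of about 150. If there is no site effect, the %TBWL interval widens by about 0.2% with full data (1.610 to 1.614) and by about 1.7% in a completer analysis with 30% random dropout. Baseline weight could be added as a covariate on other grounds; this argument does not support it.
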